#### **2.4.2** Risks

The potential risks to patients enrolled in this trial have been outlined in sections describing the potential adverse events associated with: (a) may tansine and its analog, DM1; (b) inhibition of EGFR; (c) inhibition of EGFR by anti-EGFR monoclonal antibodies; and (d) antibody-drug conjugates (ADC). Nonclinical toxicology studies have been performed in cynomolgus monkeys to evaluate potential safety issues that may emerge in patients treated with AVID100 and these studies have been utilized to define a starting dose for the first clinical study. A cohort dose escalation plan has been included to rapidly escalate the dose of AVID100 initially, but decrease the incremental increases and increase the patient sample size in subsequent cohorts. Escalation to each subsequent higher dose cohort will require demonstration of safety and tolerability in the preceding cohort until a safe recommended Phase 2 dose (R2PD) and schedule can be established. In the event of certain toxicities the infusions may be slowed, premedications or other supportive measures may be instituted, doses may be decreased, or AVID100 may be discontinued. Premedications for infusion-related reactions are not required, but can be instituted in patients who experience such adverse reactions during any cycle and, premedication for all patients may be instituted if the frequency and/or severity of AEs suggest that this would improve patient safety and the tolerability of AVID100.

Note: Effective with protocol v5.0, in order to decrease the risk of IRRs all patients will be premedicated with standard therapies prior to each infusion, at minimum through and including Cycle 4. A recommended premedication regimen is provided (see **Section 8.2**; Premedication of Study Drug-Related Toxicities).

Because of the risk of pulmonary toxicity that has been observed with ADCs and agents inhibiting EGFR, and because a single patient on the Phase 1a segment of this trial receiving a dose of 270 mg/m² developed pneumonitis considered related to AVID100, patients with a history of or evidence of interstitial fibrosis will continue to be excluded from entry into the trial. Patients will be assessed using chest CT every 6 weeks (when disease assessments are scheduled) regardless of whether these imaging studies are required for tumor assessment. Patients will also be evaluated by regular evaluation of oxygen saturation using pulse oximetry, physical exams and queries regarding all adverse events with a detailed assessment of potential

pulmonary adverse events. Pulse oximetry will be conducted prior to and following all infusions of AVID100 throughout the study, and decreases in oxygen saturation will require further evaluation. In the event of patient-reported symptoms of pulmonary toxicity or Investigator-assessed symptoms or signs of potential pulmonary adverse effects, additional studies including interval chest imaging studies will be performed. If pulmonary findings on imaging studies (e.g., evidence of pulmonary fibrosis, interstitial pneumonitis, acute respiratory distress syndrome) or clinical evidence of pulmonary adverse effects are detected, administration of AVID100 will be permanently discontinued and pulmonary consultation will be obtained to consider additional appropriate diagnostic procedures and/or therapeutic interventions.

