# 6.4. Requirements for Patient Observation

Patients will be treated on an outpatient basis, and will be evaluated and discharged from the clinic on days of scheduled study visits\*, unless hospitalization is required for other reasons or to assure patient safety.

AVID100 must be administered under close supervision in an environment where full resuscitation facilities are immediately available. IV infusions will be carefully monitored to assess safety and tolerability by qualified site medical personnel. Such personnel must be available in order to evaluate and treat any AEs, as well as to evaluate whether continued participation of the patient in the study is warranted or advisable.

- Phase 1a Dose-Escalation Cohorts: Patients will be carefully observed for a minimum of 4 hours following completion of the first administration of study drug (Day 1) for evidence of any treatment-related AE(s), and so that final Day 1 samples for post-dosing PK assessments may be obtained\*\*, and a minimum of 1 hour following completion of subsequent infusions.
- Phase 2a Expansion Cohorts: Patients will be carefully observed for a minimum of 2 hours following completion of the first administration of study drug (Day 1) for evidence of any treatment-related AE(s) \*\*, and a minimum of 1 hour following completion of subsequent infusions. *PK samples will only be collected prior to dosing on Day 1 of each cycle in the Dose Expansion Cohorts.*

At the end of each infusion, the IV line must remain in place for at least 1 hour to allow administration of IV drugs, if necessary.

Patients will be followed on an outpatient basis during the interval between each scheduled study visit.

\*Clinical and laboratory assessments will occur at the frequencies indicated (see **Section 7**; Study Assessments). In the event of an AE, assessment frequencies may be increased, as clinically indicated.

\*\*Comprehensive collection of clinical samples is critical to the conduct of this study. In situations where collection of 4h samples is logistically difficult due to clinic staff availability, the observation period may be shortened, and an "end of day" sample may be obtained at the latest practical time. Such an option is available ONLY after previous discussion with and approval by the Sponsor.

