#### 6.7.3 Evaluation Schedules

The same evaluations required during Cycle 1 of the study will be conducted during subsequent cycles, at the frequencies indicated (see **Section 7**; Study Assessments).

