## 7.2.3 Performance Status Evaluation

(To be assessed by ECOG score; see **Appendix B**; Performance Status Evaluation)

- Screening
- Cycle 1
  - o Day 1\*
- Each cycle thereafter
  - o Day 1 (prior to dosing)
- EOT
- 1M FUP
- As clinically indicated

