# 7.2.4 Vital Signs

(Vital signs [VS] to include temperature, pulse, respiratory rate, blood pressure[BP], and oxygen saturation by pulse oximetry)

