### Phase 2a Expansion Cohorts

- Screening
- Cycle 1
  - o Day 1
    - Prior to SOI
    - EOI (± 5 min)
- Each cycle thereafter
  - o Day 1
- EOT
- 1M FUP
- As clinically indicated

\*\*Comprehensive assessment of vital signs is critical to the conduct of this study. In situations where an assessment at 4h after EOI is logistically difficult due to clinic staff availability, the observation period may be shortened, and an "end of day" assessment may be obtained at the latest practical time. Such an option is available ONLY after previous discussion with and approval by the Sponsor.

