### 7.2.5 Physical Examination

(Complete at screening including height, weight, general appearance, skin, ears, eyes, nose, throat, neck/thyroid, chest, heart, abdomen, musculoskeletal system, peripheral pulses, lymph nodes, neurologic and mental status; directed thereafter, must include weight\*\* and pulmonary assessment\*\*\* at each visit)

- Screening
- Cycle 1
  - o Day 1\*
- Each cycle thereafter
  - o Day 1 (prior to dosing)
- EOT

\*SOI-Start of Infusion; EOI-End of Infusion

- 1M FUP
- As clinically indicated
- \* Need not be assessed prior to Cycle 1 if  $\leq 7$  days since screening
- \*\* Dose adjustments may be made in the event of noted weight change ( $\pm 10\%$  [less at the site's discretion or if required by institution procedures]).
- \*\*\* Pulmonary findings will be evaluated in detail at each visit by the PI (or physician designee); evaluation to include review of pulmonary symptoms including but not limited to: cough, sputum production, hemoptysis, wheezing, dyspnea, dyspnea on exertion, chest pain, and/or chest pain associated with respirations.

Note: See Appendix H (Recommendations for Management of Keratitis and Rash) for dose modification instructions for rash

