# APPENDIX A Study Assessments

			TABI	LE 7:	: STU	J DY A	ASSE	SSMEN	TS SCH	IEDULE	,				
			YCLE 1				CYCL			BSEOUEN		EOT < 10d	1M FUP*	Extended	As
STUDY ASSESSMENTS	Screen	D1	D2	D4 +/- 1d	D8	D1	D8	End of Cycle 2	D1	D8	End of Even Number Cycles d	after decision to dis-continue	30 d (+7) after last dose	Follow Up* if OR or SD at EOT	Clinically Indicated
CONSENT AND MEDICAL HISTORY															
Informed Consent  / Eligibility Assessment	X														
Past Medical History	X														
History of Primary Malignancy 	X														
SAFETY ASSESSMENTS (1) (screening asses	sments withi	n 14 days prior to	o first sti	ıdy dru	g dose										
Medication Survey 	X									0 days after					
AE Assessments 			t through	30 day	ys after l	ast dose	; throug	h 3 months	or 6 months	to 2 years)	follow-up if associa				 
ECOG PS Evaluation	Х	X a				X			X			х	X		X
Phase 1a: Vital Signs 	x	SOI; EOI; 2, 4h after EOI	х	х		х			x			x	х		х
Phase 2a: Vital Signs 	X	SOI, EOI				X			X			х	X		X
Physical Exam/to include weight and	X	x a				х			x			x	х		x
pulmonary assessment 															_ ^
Hematology Panel 	X	x a		X	X	X	X		X	X		X	X		X
Serum Chemistry Panel 	X	x a		X	X	X	X		X	X		X	X		X
Coagulation Panel 	X	X a		X	X	X	X		X	X		х	X		Х
Urinalysis 	X	x a		X	X	X	X		X	X		х	X		Х
ADA to AVID100 		X				X			X			х	X		xe
Pregnancy Testing  (w/in 2 days of I st dose)	X	X										х			Х
ECG (12-lead) 	x	SOI, EOI, 30 min after EOI										x			x
SAFETY ASSESSMENTS (2) (screening asses	sments withi	n 28days (+/- 2)	prior to	first sti	udy druį	g dose p	rovided	no antineo	plastic thera	py has been	delivered between a	ssessment and	first dose of s	tudy drug)	
Ophthalmology Exam 	X										End of C2 only	X			х
MUGA Scan or Echo 	X											X			X
Pulmonary function tests 	X											x			X
Chest radiography (PA and lateral)	X											x			X
DISEASE ASSESSMENTS (screening assessm	ents within 2	28 days (+2d) prie	or to first	t study	drug do	se)									
Phase 1a only: Document EGFR positivity 	optional														
Phase 2a only: Document EGFR positivity 	required														

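### Section 2.4.2 promises oxygen saturation before and after every infusion, but the schedule times that pair only on Cycle 1 Day 1

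*Combined protocol and SAP*

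**What the plan says.** Section 2.4.2 (Risks) makes an unqualified commitment: "Pulse oximetry will be conducted prior to and following all infusions of AVID100 throughout the study". It adds that decreases call for further evaluation. The paragraph gives its reason as pulmonary toxicity seen with antibody-drug conjugates and EGFR inhibitors, together with one AVID100-related pneumonitis at 270 mg/m² in Phase 1a.

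Oximetry has no row of its own in the schedule. Section 7.2.4 places it within vital signs: "Vital signs [VS] to include temperature, pulse, respiratory rate, blood pressure[BP], and oxygen saturation by pulse oximetry". Footnote 5 to Table 7 (Appendix A) does the same. The timing of vital signs is therefore the timing of oximetry. Section 7.2.4 gives:

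- **Cycle 1 Day 1, Phase 1a:** before the start of infusion, at its end (± 5 min), and 2 and 4 hours after that.
- **Cycle 1 Day 1, Phase 2a:** before the start of infusion and at its end (± 5 min).
- **Later cycles, both phases:** under "Each cycle thereafter", a bare Day 1 entry with no time relative to the infusion.
- **Both phases:** end of treatment, 1-month follow-up, and when clinically indicated.

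Table 7 agrees. Its row "Phase 2a: Vital Signs" shows start and end of infusion in the Cycle 1 Day 1 column, then a plain X on Day 1 of Cycle 2 and of subsequent cycles. The Phase 1a row follows the same pattern.

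**The concern.** The stated safeguard and the schedule meant to deliver it do not match. Sites and monitors work from Section 7 and Table 7. A site that does exactly what those say falls short of Section 2.4.2 at every infusion after the first.

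The missing quantity is the within-infusion change in saturation, which bears on acute reactions. Section 8.2.1 lists shortness of breath, wheezing and bronchospasm among the signs of an infusion-related reaction, and Section 6.6.1.1 treats the risk as continuing by requiring premedication before each dose. Appendix G lets a patient whose infusion was prolonged return to a shorter one after at least two doses free of infusion-related toxicity. Those doses normally fall in Cycle 2 or later, where no post-infusion saturation is scheduled to inform the judgement.

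There is a second, smaller loss. Because the later reading is untimed, it may be taken before the infusion at one cycle and after it at another. A cycle-to-cycle comparison can then mix the two.

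**Working it through.** The plan states no figure to reproduce. The check is a comparison of texts and a count.

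**1. Readings promised and scheduled.** For a patient with n infusions, counting readings on infusion days:

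- Promised by Section 2.4.2: 2n.
- Scheduled in Phase 2a: 2 + (n − 1) = n + 1.
- Scheduled in Phase 1a: 4 + (n − 1) = n + 3.
- Infusions with no scheduled before/after pair, either phase: n − 1.

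| n | Where n comes from | Promised | Phase 2a | Phase 1a | Infusions without a pair |
|---|---|---|---|---|---|
| 2 | Estimated average participation of 6 weeks, notes to Table 9 | 4 | 3 | 5 | 1 of 2 (50%) |
| 5 | Phase 2a Cycle 5 PK visit, Section 7.5.1 | 10 | 6 | 8 | 4 of 5 (80%) |
| 8 | Phase 1a patient with a laboratory event in Cycle 8, Section 2.3.2.1 | 16 | 9 | 11 | 7 of 8 (87.5%) |

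The Phase 1a total exceeds the promised number at n = 2 only because Cycle 1 Day 1 carries four readings. The number of pairs is still 1.

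**2. Phase 2a as a whole.** With about 60 patients and n = 2, there are 60 × 2 = 120 infusions, of which 60 × (2 − 1) = 60 have no pair. The footnote to the Phase 2a adverse-event table counts 13 patients at 15 April 2020, before this version (30 May 2020). If those 13 are set aside, 60 − 13 = 47 patients remain, with 47 × 2 = 94 infusions and 47 without a pair. The proportion does not change.

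**3. Does another provision supply the pair?**

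- Section 6.7.3 says "The same evaluations required during Cycle 1 of the study will be conducted during subsequent cycles, at the frequencies indicated" and refers to Section 7. The frequencies indicated there are the bare Day 1 entries, so it leads back to the gap.
- Section 6.4 requires observation for "a minimum of 1 hour following completion of subsequent infusions", and Table 7 has a post-infusion monitoring row marked in later cycles. Neither names a measurement.
- Readings taken when clinically indicated are unscheduled and cannot meet a commitment covering all infusions.

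**4. Is the missing time only drafting style?** No. Later-cycle timing is printed where it is wanted. Performance status has "Day 1 (prior to dosing" in its later-cycle entry, as do physical examination and the laboratory panels (Sections 7.2.5 to 7.2.9). Phase 1a PK gives start and end of infusion in every later cycle (Section 7.5.1). ECGs give the same two times for the four cycles after a Cycle 1 QTc abnormality (Section 7.2.12). Section 7.2.4 and Table 7 also agree with each other, so a fault in reading the table is unlikely.

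**5. Background rate of reactions.** Table 1 gives infusion reactions in 5 of 24 Phase 1a patients: 5/24 = 20.8%, four Grade 2 and one Grade 3.

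**The case against.** The strongest reply is that the schedule is silent and does not contradict Section 2.4.2. An untimed Day 1 entry does not forbid two readings, Section 2.4.2 is itself protocol text, and items meant only for before dosing are labelled so while vital signs are not. This does not rescue the schedule. Section 7.2.4 spells out the pair for Cycle 1 and drops it for later cycles, so the natural reading is a single assessment. It remains an inference that sites would take only one, and the counts above rest on it.

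Several points about the size of the harm do stand:

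- The oximetry sentence was written for pulmonary toxicity, for which a fall between cycles is the more useful signal. One Day 1 reading per cycle remains, with readings at end of treatment and 1-month follow-up, a detailed pulmonary assessment at each visit, and chest imaging at every even-numbered cycle.
- Infusion reactions are graded and managed clinically under supervision, and the rechallenge rule contains no saturation criterion.
- The 20.8% is not split by cycle of onset. At least three of the five reactions came with infusions shorter than the present 2 hours: the Grade 3 in Cohort 3 (1 hour) and two Grade 2 in Cohort 4 (1.5 hours). It shows that reactions occur, not how often they would from Cycle 2 under current conditions.
- The values n = 5 and n = 8 are illustrations.

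These points limit the consequence. They do not remove the mismatch.

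**Conclusion.** The concern holds. As written, the schedule delivers the before/after saturation pair at 1 of n infusions in both phases, against the n of n that Section 2.4.2 promises. The shortfall is 50% of infusions at the protocol's two-cycle average and 80% at five cycles. This assumes that sites read a bare Day 1 entry as one reading and that infusions are given once per cycle.

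The consequence is moderate. The change across an infusion is not scheduled from Cycle 2, and the single reading that remains has no fixed relation to dosing. No rule for dose-limiting toxicity, treatment discontinuation or stopping accrual uses an oximetry threshold, so those decisions are unaffected. The mismatch should be corrected because it concerns a stated patient-safety measure and is cheap to mend.

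**What to change.** In Section 7.2.4, for both phases, and in the two vital-signs rows of Table 7, replace the later-cycle Day 1 entry, at least for oximetry, with a reading before the start of infusion and one at its end (± 5 min), as already written for Cycle 1 Day 1. If the sponsor does not intend paired readings after Cycle 1, amend the sentence in Section 2.4.2 instead. One of the two texts has to change.

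The cost is schedule wording plus one oximeter reading per infusion from Cycle 2, which fits into the post-infusion observation hour that Section 6.4 already requires. At two cycles per patient this is 60 × 1 = 60 extra readings across Phase 2a.

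A separate, minor alignment could go into the same amendment: Sections 2.4.2 and 3.3 name CT for on-treatment chest imaging, while Sections 7.3.4 and 7.4.3 accept CT or MRI. It has no bearing on saturation.

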Criteria for Treatment Discontinuation	Patients will be discontinued from further treatment with study drug in the event of any of the following:  1. Patient must be permanently discontinued in the event of any major, potentially irreversible organ system DLT, including:  • Pulmonary toxicity defined as:  ○ Evidence of pulmonary fibrosis, any grade  ○ Reduction of forced vital capacity (FVC) or DL CO ≥ Grade 3  • Neurotoxicity defined as peripheral neuropathy ≥ Grade 3  • Nephrotoxicity defined as:  ○ Acute kidney disease ≥ Grade 3 (i.e., creatinine > 3 × baseline or > 4.0 mg/dL)  ○ Chronic kidney disease ≥ Grade 3 (i.e., estimated glomerular filtration rate [eGFR] or creatinine clearance [CrCl] 29-15 mL/min/1.73 m²)  ○ Proteinuria ≥ Grade 3 (i.e., ≥ 3.5 g/24 hours)  • Hepatotoxicity suggestive of drug-induced liver injury, as characterized by the following 3 criteria:  ○ AST and/or ALT elevation > 3 × ULN (or > 3 × baseline if elevated at study entry as allowed by study eligibility criteria)  ○ Total bilirubin > 2 × ULN without initial findings of cholestasis (i.e., no elevation in serum ALP)  ○ No explanation for the above findings, such as: viral hepatitis A, B, or C; preexisting or acute liver disease; or another drug capable of causing the observed injury

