	
 
Adapted from: Hy's Law. Drug-induced liver injury: premarketing clinical evaluation. Guidance for Industry. U.S. Department of HHS, FDA, CDER, CBER, 2009.
 
Any other DLT considered by the Investigator to require treatment discontinuation. Note: Patients experiencing a DLT not listed in #1 above may continue at a reduced dose if there is evidence of an OR, SD, or other clinical benefit, and ONLY following discussion with the Sponsor's Medical Monitor(s).
 
Another AE not meeting the criteria for a DLT, yet considered by the Investigator to require treatment discontinuation.
 
Documented progressive disease at any time during the study
 
Treatment failure not meeting the criteria for progressive disease, but considered by the Investigator to require treatment discontinuation.
 
Requirement for a significant surgical procedure
 
An intercurrent illness which, in the opinion of the Investigator, would prevent completion of study-related evaluations
 
Significant deviation from the protocol or eligibility criteria. Such patients will be considered protocol violations and will be discontinued from treatment
 
Pregnancy
 
Noncompliance with study or follow-up procedures
 

Follow-up	
 
11. Patient withdrawal of consent and election to discontinue treatment with study drug. (Patients may leave the study at any time for any reason if they wish to do so, without any consequence.)
 
12. Termination of the study by the Sponsor
 
Any other reason which, in the opinion of the Investigator, would justify treatment discontinuation.
 
End of Treatment (EOT) evaluations to be conducted within approximately 10 days following the decision to discontinue the patient from further treatment
 
I Month Follow-up (1M FUP) evaluations to be conducted approximately 30 days (+7 days) following the last dose of study drug.
 
If an observed toxicity thought to be associated with study drug has not resolved by the 1M FUP evaluation, an additional follow-up AE assessment will be conducted approximately 3 months (may be repeated at 6 months if needed) following the last dose of study drug, if feasible, in order to confirm that the event has either resolved,
 

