#### **Study Assessments**

For safety, patients will be monitored throughout the treatment and 1 month follow-up period for evidence of AEs, including changes in clinical status, laboratory data, ECG findings, and either MUGA scans or echocardiograms in patients with a history of CHF. Evaluation of patients for interstitial pulmonary fibrosis or other pulmonary disorders will include evaluation of related signs and symptoms, reported adverse effects, pulse oximetry, pulmonary function tests, and radiographic imaging of the chest (X-ray and CT); evidence of pulmonary fibrosis of any grade at any point in the trial will result in immediate discontinuation from treatment with study drug. Patients will also be evaluated for evidence of antibody formation to AVID100. Patients experiencing a DLT regarded as associated with study drug at any point during treatment will either be discontinued from treatment with study drug, or may continue if there is evidence of an OR, disease stabilization, or other clinical benefit, but must do so at a reduced dose of AVID100 (see Section 8.3.2; Dose Reduction), and ONLY following discussion with the Sponsor's Medical Monitor(s). Patients may not be retreated following the occurrence of a DLT until

retreatment criteria have been met. Only DLTs occurring during Cycle 1 will be used to make determinations regarding dose escalation and tolerability. Exceptions to continuing on study at a reduced dose include evidence of pulmonary, neuro-, ocular, nephro-, or hepatotoxicity as detailed in **Section 9.1** (Criteria for Treatment Discontinuation). In such instances patients must be permanently discontinued from treatment with study drug.

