# 8.3.2.1. Delay Between Dosing

If indicated, the period between any 2 scheduled doses may be extended to allow for amelioration of the toxicity. However, if any observed Grade 3 or Grade 4 toxicity thought to be associated with study drug results in delay of dosing beyond 2 weeks of the next scheduled dose, regardless of whether the criteria for DLT are met, the event will be considered a DLT, necessitating that the patient either have their dose of study drug reduced or be discontinued from further treatment with study drug.

For toxicities not meeting the protocol definition of DLT that are to be managed by dose interruption, dosing may be restarted at the same or a reduced dose(s), as clinically indicated. However, for a DLT that is managed by dose interruption, administration of study drug MUST be restarted at a reduced dose once retreatment criteria have been met (see **Section 6.7.1**; Retreatment Guidelines).

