### 9.1. Criteria for Treatment Discontinuation

Patients will be discontinued from further treatment with study drug in the event of any of the following:

- 1. Patient must be permanently discontinued in the event of any major, potentially irreversible organ system DLT, including:
  - Pulmonary toxicity defined as:
    - o Evidence of pulmonary fibrosis, any grade
    - o Reduction of forced vital capacity (FVC) or DLco  $\geq$  Grade 3
  - Neurotoxicity defined as peripheral neuropathy ≥ Grade 3
  - Any ocular toxicity  $\geq$  Grade 3
  - Nephrotoxicity defined as:
    - Acute kidney disease  $\geq$  Grade 3 (i.e., creatinine  $> 3 \times$  baseline or > 4.0 mg/dL)
    - o Chronic kidney disease ≥ Grade 3 (i.e., estimated glomerular filtration rate [eGFR] or creatinine clearance [CrCl] 29-15 mL/min/1.73 m²)
    - o Proteinuria  $\geq$  Grade 3 (i.e.,  $\geq$  3.5 g/24 hours)
  - Hepatotoxicity suggestive of drug-induced liver injury, as characterized by the following 3 criteria:
    - AST and/or ALT elevation  $> 3 \times ULN$  (or  $> 3 \times$  baseline if elevated at study entry as allowed by study eligibility criteria; see **Section 4.3.1** #7)
    - Total bilirubin  $> 2 \times ULN$  without initial findings of cholestasis (i.e., no elevation in serum ALP)
    - No explanation for the above findings, such as: viral hepatitis A, B, or C; preexisting or acute liver disease; or another drug capable of causing the observed injury

Adapted from: Hy's Law. Drug-induced liver injury: premarketing clinical evaluation. Guidance for Industry. U.S. Department of HHS, FDA, CDER, CBER, 2009.

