# **FORBIUS**

2. Any other DLT (see **Section 6.8.3**; Definition of DLT) considered by the Investigator to require treatment discontinuation.

Note: Patients experiencing a DLT not listed in #1 above may continue at a reduced dose if there is evidence of an OR, SD, or other clinical benefit, provided protocol stipulated retreatment criteria delineated in **Section 6.7.1** (Retreatment Guidelines) have been met, and ONLY following discussion with the Sponsor's Medical Monitor(s)).

3. Another AE not meeting the criteria for a DLT, yet considered by the Investigator to require treatment discontinuation.

Note: AEs resulting in a patient's permanent discontinuation from study treatment, regardless of seriousness or relationship to study drug, MUST be reported promptly to the Sponsor (or designee).

- 4. Documented progressive disease at any time during the study
- 5. Treatment failure not meeting the criteria for progressive disease, but considered by the Investigator to require treatment discontinuation.
- 6. Requirement for a significant surgical procedure

Note: Patients requiring a minor surgical procedure (e.g., port placement, skin abscess drainage) may continue at the Investigator's discretion following discussion with the Sponsor's Medical Monitor(s). A brief interruption in therapy may be considered.

- 7. An intercurrent illness which, in the opinion of the Investigator, would prevent completion of study-related evaluations
- 8. Significant deviation from the protocol or eligibility criteria. Such patients will be considered protocol violations and will be discontinued from treatment
- 9. Pregnancy
- 10. Noncompliance with study or follow-up procedures
- 11. Patient withdrawal of consent and election to discontinue treatment with study drug. (Patients may leave the study at any time for any reason if they wish to do so, without any consequence.)
- 12. Termination of the study by the Sponsor
- 13. Any other reason which, in the opinion of the Investigator, would justify treatment discontinuation. In such a case, the Investigator's reason for treatment discontinuation must be recorded on the appropriate page of the eCRF.

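### Section 2.4.2 requires a permanent stop for imaging findings such as interstitial pneumonitis or ARDS, but the stopping list in Section 9.1 and the synopsis omits them and leaves conditional routes to re-dosing

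*Combined protocol and SAP*

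**What the plan says.** **The mandate.** Section 2.4.2 (Risks) cites a related pneumonitis at 270 mg/m² in Phase 1a and schedules chest CT every 6 weeks. It gives fibrosis, interstitial pneumonitis and ARDS as examples of imaging findings, adds clinical evidence of pulmonary adverse effects, and says that if any of these is detected "administration of AVID100 will be permanently discontinued and pulmonary consultation will be obtained". It states no condition on grade, relatedness or clinical benefit.

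**The stopping list.** Section 9.1 #1 requires permanent discontinuation for major, potentially irreversible organ system DLTs. Its pulmonary item has two parts: "Evidence of pulmonary fibrosis, any grade", and an FVC or DLco reduction of Grade 3 or higher. The synopsis introduces the same two parts with the words "Pulmonary toxicity defined as". Section 8 sends the reader to Section 2.4 for anticipated toxicities, but to Section 9.1 for events requiring discontinuation.

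**The permissions.** The note to Section 9.1 #2 begins: "Patients experiencing a DLT not listed in #1 above may continue at a reduced dose if there is evidence of an OR, SD". The note accepts any further kind of clinical benefit too, and it is subject to the retreatment criteria and discussion with the Medical Monitor. The synopsis has the same note without the retreatment criteria. Section 8.1 gives the same permission with the retreatment criteria. For non-DLT events, Section 8.3.2.1 has a restart sentence that begins: "For toxicities not meeting the protocol definition of DLT that are to be managed by dose interruption, dosing may be restarted at the". The restart dose may be unchanged or lowered.

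**The summary.** Section 3.3 has this clause: "Exceptions to continuing on study at a reduced dose include evidence of pulmonary, neuro-, ocular, nephro-, or hepatotoxicity as detailed in". The reference given there is to Section 9.1. For an immediate stop it names only fibrosis: "evidence of pulmonary fibrosis of any grade at any point in the trial will result in immediate discontinuation from treatment with study drug".

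**The concern.** Chest CT is scheduled in order to find these lung events, so sites need one rule for what to do when they appear. Section 2.4.2 gives an unconditional rule. The sections a site would use to manage a patient give a narrower list and allow treatment to resume in some cases that 2.4.2 rules out.

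At stake is re-exposure of an individual patient after a serious lung toxicity already seen in this trial. The protocol also describes interstitial lung disease for anti-EGFR antibodies (Section 2.3.1.3) and for the DM1 conjugate ado-trastuzumab emtansine (Section 2.3.1.4). Two of the three Phase 2a tumor types, SCCHN and Sq-NSCLC, fall in groups that Phase 1a admitted only after review of smoking history, lung function and imaging (Section 4.2, criterion 5).

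**Working it through.** The plan gives no figure to reproduce, so the check is mainly a comparison of rules.

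**Step 1: which pulmonary events each section stops.** Section 2.4.2 covers imaging findings of any grade, with three named examples, plus clinical evidence. Sections 9.1 #1 and the synopsis each have two criteria. Neither is interstitial pneumonitis, ILD or ARDS.

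**Step 2: follow an event with no fibrosis and no Grade 3 or higher FVC/DLco reduction.**

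| Event | Section 2.4.2 | Management sections |
|---|---|---|
| Related Grade 3 pneumonitis | Permanent stop | DLT under 6.8.3 item 2, since pneumonitis is not among its exceptions. Not listed in 9.1 #1, so the 9.1 #2 note, the synopsis note and 8.1 allow a reduced dose on conditions |
| Related Grade 1-2 pneumonitis | Permanent stop | Not automatically a DLT, so outside the 9.1 #1 heading. If managed by interruption, 8.3.2.1 allows restart at the same or a reduced dose |

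In the second row, Section 6.7.1 asks that ongoing events be at Grade 1 or lower, back to baseline, or resolved. A Grade 1 event already meets that criterion.

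**Step 3: does another section close the gap?**
- Section 3.3 limits its pulmonary exception to what 9.1 details, so it inherits the gap.
- Section 6.7.5 bars retreatment after a toxicity that required permanent discontinuation, but cites only 9.1 #1.
- Exclusion 11 (Section 4.3.1) covers ILD or fibrosis on imaging, including during study. Section 9.1 #8 discontinues patients for significant deviation from eligibility. Together they give an indirect stop for ILD. The pneumonitis and ARDS bullet of exclusion 11 covers history only.

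**Step 4: what the visible data show.** Table 1 has N = 24 and lists one pneumonitis, in the Grade 3 row. Section 2.4.2 places the related case at 270 mg/m². Section 2.6 gives 7 patients treated at that dose, the highest studied, so 24 − 7 = 17 received 220 mg/m² or less.
- At 270 mg/m²: 1/7 = 14.3%, exact (Clopper-Pearson) 95% CI 0.4% to 57.9%.
- At 220 mg/m² or below: 0/17. The upper limit of the two-sided exact 95% interval is 1 − 0.025^(1/17) = 19.5%.

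These figures show that the event has occurred. They neither establish nor exclude a material rate at 220 mg/m².

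**The case against.** The strongest reply has four parts.

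1. **A permission does not override a mandate.** Section 2.4.2 says the drug will be stopped. Section 8.3.2.1 applies only to toxicities managed by interruption, and 2.4.2 says these are not. This is a fair reading, but the available text does not say which section prevails, and Section 8 points to 9.1 for stopping.

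2. **Safeguards exist.** Continuation after a DLT needs evidence of benefit and Medical Monitor discussion, and 9.1 and 8.1 also require the retreatment criteria. Section 6.10 requires prompt reporting of DLTs and dose modifications. The Investigator may stop at any time under 9.1 #2, #3 or #13. All of this stands and narrows the point, but discretion and consultation are not the unconditional stop in 2.4.2.

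3. **The list in 9.1 #1 is open, because it is introduced as inclusive.** That may hold for organ systems. Pulmonary toxicity, however, is defined by its two parts, and the #2 note turns on whether a DLT is listed in #1. An open reading would still cover only DLTs.

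4. **Exclusion 11 with 9.1 #8 already stops ILD.** This is a real route, but an indirect one. Section 9.1 does not cite exclusion 11, and the route does not clearly reach pneumonitis or ARDS arising on study.

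A reader might infer that the protocol simply permits re-dosing after pneumonitis, or that a patient was re-dosed. The documents support neither. No section directs re-dosing and 2.4.2 forbids it. The account of how the Phase 1a case was handled, and part of the Phase 2a adverse event table, are not in the available text.

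**Conclusion.** The conflict is real: an unconditional stop in Section 2.4.2 against a narrower stopping list and conditional permissions in 9.1, the synopsis, 8.1 and 8.3.2.1. It affects related pneumonitis, ILD or ARDS without fibrosis and without a Grade 3 or higher FVC/DLco reduction. For Grade 3 events the gap is limited by the benefit requirement and Medical Monitor discussion. For Grade 1-2 events it depends on the site choosing interruption.

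This should be corrected on grounds of patient safety. It does not touch DLT counts, the MTD or the efficacy analyses. The one visible case was at 270 mg/m², a dose declared above the MTD, so no event rate at 220 mg/m² and no Phase 2a count is claimed. The conclusion assumes that 2.4.2 is meant to bind. If it is not, its wording misleads and still needs correction.

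**What to change.** 1. Add to Section 9.1 and to the synopsis a separate mandatory item, outside the DLT heading of #1: *Interstitial pneumonitis/ILD or ARDS, any grade: permanent discontinuation.* If the sponsor limits it to drug-related events, the amendment should say that this narrows 2.4.2.
2. Exclude that item from the reduced-dose permissions in the 9.1 #2 note, the synopsis note and Section 8.1, and from the restart sentence in 8.3.2.1.
3. Extend the retreatment bar in Section 6.7.5 to the new item.
4. Add the same findings to the fibrosis sentence in Section 3.3.
5. Cross-reference 2.4.2 to 9.1. If the ungraded trigger of clinical evidence of pulmonary adverse effects is replaced, state that this narrows 2.4.2 and why.

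This is text only, in seven places: 9.1, synopsis, 8.1, 8.3.2.1, 6.7.5, 3.3 and 2.4.2. Section 9.1 and the synopsis each need two edits. The DLT definition in 6.8.3 need not change. The cost is that a few patients with recovered or low-grade pneumonitis and clinical benefit could not resume, which 2.4.2 already requires. Cutting 2.4.2 back to the current 9.1 list would also remove the conflict, but it would relax a stated safety rule and need a stated reason.
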